## 7 SAFETY ASSESSMENTS

Since the intervention is a coordinated care program, risk of study-related adverse events is expected to be minimal. Expected serious adverse events include hospitalizations and deaths but these are in line with what would be expected for this elderly population. We will not be carrying out medical interventions or treatments as part of the pilot study. In some cases, participants may be referred to their primary care provider or other health professional regarding pharmacologic therapy or other therapies. Final decisions about treatment will be made by these physicians or other qualified health providers. The MCC may recommend care strategies that may incur additional costs. Neither the PLWD nor the care partner will be obligated to seek or accept these services. There are potential risks of discomfort about answering personal questions during the evaluation. There are potential risks to confidentiality should the findings of the assessment become known to others.

## 7.1 Minimization of Risks

To minimize discomfort or frustration that may occur during the needs assessment, participants may decline to answer any questions, take frequent breaks, or stop the assessment. The results of the dementia evaluation will be kept confidential and shared only as needed with members of the study team and with the primary care provider as part of the patient's care. Permission for the MCC to make referrals to various agencies or services is necessary for study participation. However, referrals made by the MCC will be in collaboration (agreed upon) with the PLWD/care partner and will follow best practices, including care options or strategies that are available in the community. These recommendations should provide beneficial outcomes in the aggregate. At any time, the PLWD/Care Partner may choose to refuse a service or discontinue their participation in the pilot study. The quality of their medical care will not be adversely affected if they decide to refuse a service and/or withdraw from the study. (See Program Information Sheet, Appendix C.)

Confidentiality of data will be ensured in several ways. Anonymous data collection forms will be used, with unique study identifying numbers and will be maintained in a secure location, and we will maintain a source document chart for each participant that will contain contact information, clinical information, and notes. Source documents will be password-protected and shared with the study team using a secure drop box link. Data entry will be performed concurrent with fieldwork via appropriate data entry forms that will be created with embedded validation criteria. The database will be kept locally at the study sites on secure servers which offer routine off-site back up.

## 7.2 Plans for Reporting Unanticipated Problems or Study Deviations

The entire study team will be trained on immediately reporting any adverse events, alerts (e.g., hazardous or emergency situations), or study deviations to the PI. See Chart A below for types of possible alerts that may be encountered and types of actions to be taken. See the DSMP below. If any serious possible or potentially study-related adverse events arise, the PI will notify the IRB, the DSMB Chair, and IMPACT SO, and others as stated in the data safety monitoring plan (DSMP), within 48 hours of learning of the events and will provide a safety report describing the adverse event and actions taken by the study. See the DSMP below. Deaths will be reported within 24 hours, per the DSMP. Additionally, the PI will keep a log of adverse events in compliance with IRB policies and per direction from the DSMB and whether the event is unrelated, possibly related, or probably related to the study or intervention. Study deviations will be reported when discovered along with any corrective actions taken by the study to the IRB, DSMB Chair, IMPACT SO, and others as stated in the DSMP. Routine adverse events (such as non-intervention related events such as death) will be reported within 24 hours and summarized and shared with appropriate individuals per the DSMP. At the start of the study, participants and care partners will be instructed to report serious adverse events to the MCC who in turn will notify the PI, who will notify the appropriate persons per the DSMP. Serious adverse events, discovered either by the clinical team in routine activities or ones which the family report, will be presented to the PI, the Is, and study team who together with the available data will make a determination as to whether the event is unrelated, possibly related, or probably related to the study intervention. Because this is a guideline-driven psychosocial intervention which seeks to provide coordinated care to meet the care needs of individuals with dementia living in the community, we do not anticipate adverse events beyond the background rate for this elderly population.

## 7.3 Chart A. Specific Alerts and Actions Taken

ALERT	ACTION TAKEN
Medical emergency:	

 
-Chest pains
 
- Excessive bleeding
 
- Fall and cannot get up
 
- Difficulty breathing
 
	
If MCC or clinic staff encounters this situation over the telephone, we identify whether another individual is in the home, the person is put on hold, and we call 911 immediately and stay on phone until external help arrives. If situation occurs within home, then MCC calls 911 immediately, and stays with participant until help arrives. PI is informed within 24 hours of the event. Clinical study staff member ([name]) then contacts individual as a follow-up within two days.
 
MCC completes alert form and provides to study coordinator and PI.

Suicidal ideation, threats to hurt self or others	
If MCC encounters a situation in which the person (PLWD or CP) threatens to hurt self imminently/immediately, then MCC stays with person (on phone or in home), calls 911 and stays with individual until help arrives. If the person (PLWD or CP) is determined to not be an immediate threat to self, then the person is actively encouraged to contact physician or contact is made for the person if they allow that to occur. A verbal contract or agreement is obtained with the person that they will not hurt themselves. The MCC also informs the person that a member of the research team will be contacting him/her shortly to follow-up. Immediately at the conclusion of the interview, the PI is notified of the situation. The clinical study staff member ([name]) will contact the person as soon as possible to obtain further information and encourage immediate action to be taken (e.g., physician referral). Clinical study staff and PI further consult about case within 24 hours of event with medical team to determine what further actions should be taken.
 
MCC completes alert form and provides to study coordinator and PI.

Evidence of abuse	
Evidence of physical abuse is as follows:
 
1) CP or PLWD states to MCC that abuse occurs; or 2) MCC observes physical evidence (black eye, black and blue marks on arms/legs).
 
MCC informs participant or CP that a senior member of the research team will contact him/her later that day. MCC informs PI immediately upon completion of interview or intervention session. Clinical study staff member contacts participant to obtain further information. Participant is strongly encouraged to call his/her physician and/or Adult Protective Services (phone number will be provided). Based on the situation, the designated clinical study staff may notify Adult Protective Services and/or clinical study team members for consultation.
 
MCC completes alert form and provides to study coordinator and PI.

Unlocked gun in home	
If this is discovered on-site, the MCC notifies study coordinator within 24 hours of learning of gun in home. Study coordinator (or

	
designate) contacts person immediately to obtain further information and work on plan for removal, dismantling or storage of gun in locked cabinet. Study coordinator (or designate) provides education as to the potential danger of having a gun in home with a person with dementia. If participant keeps a loaded gun in the home, he/she is informed that we cannot go into the home until it is removed, dismantled, or locked in an inaccessible location. If alert is identified prior to enrollment visit, the person is not enrolled into the study until gun has been removed or dismantled or stored in locked area. If discovery of gun occurs after person has been enrolled, he/she is informed that they will be discontinued from study until gun has been removed, dismantled, or stored locked. MCC completes alert form and provides to study coordinator and PI.


Extreme Home Hazards
 
 
-Exposed electrical
 
-External door missing or cannot be locked
 
-Ceiling, floors caved in
 
-No temperature control (no air or heat – must be extreme)
 
-Major infestation
 
	
MCC notifies study coordinator within 24 hours. If alert is identified prior to enrollment, the individual is not enrolled in study until home hazard is addressed. If situation is discovered after person is enrolled in study, the MCC works on resolving the situation with the family caregiver but does not make home visits until the environment is safe.
 
MCC completes alert form and provides to study coordinator and PI.

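### Chart A's alert row covers threats to self or others, but states its 911 step only for an imminent threat to self

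*Combined protocol and SAP*

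**What the plan says.** Section 7.2 refers the study team to Chart A for the alerts they may meet and how to respond. The row at issue is labelled "Suicidal ideation, threats to hurt self or others" and applies to the PLWD and the care partner alike. Its action text has two branches.

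- **Urgent branch.** If the person "threatens to hurt self imminently/immediately, then MCC stays with person (on phone or in home), calls 911", the MCC remains until help arrives.
- **Lower-urgency branch.** If the person "is determined to not be an immediate threat to self, then the person is actively encouraged to contact physician", or allows the contact to be made for them, two further steps follow: "A verbal contract or agreement is obtained with the person that they will not hurt themselves", and "The MCC also informs the person that a member of the research team will be contacting him/her shortly to follow-up".

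The row then sets out escalation: "Immediately at the conclusion of the interview, the PI is notified of the situation"; a clinical study staff member "will contact the person as soon as possible to obtain further information and encourage immediate action to be taken"; and that staff member and the PI "further consult about case within 24 hours of event with medical team to determine what further actions should be taken". The MCC also completes an alert form.

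**The concern.** The label brings threats against other people into the row, but the action text does not mention others again. MCCs work in homes and by telephone or video, so a PLWD or care partner could threaten someone else during an encounter, and the person threatened could be the PLWD. Section 10.3.4 commits the team to strict adherence to the protocol, so the wording of the response matters. At stake is the safety of participants and of the people around them in a foreseeable emergency. No estimate, test or data item is involved.

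**Working it through.** No arithmetic applies. The check sets the row's label against its conditions, then looks for text elsewhere that closes the gap.

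**Step 1: the row's logic.** Let S be an imminent threat to self and O an imminent threat to another person. The label covers both. The urgent branch depends on S and the lower-urgency branch on not-S. O enters neither condition.

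| Case | Literal reading | Branches read as self-harm only |
|---|---|---|
| S, with or without O | 911, stay until help arrives | 911, stay until help arrives |
| Neither S nor O | Physician branch | Physician branch if the concern is self-harm |
| O without S | Physician branch | No immediate protective step |

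The third case is the problem. The verbal agreement does not help, because it too concerns self-harm only.

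**Step 2: what still applies in the third case.** On both readings the PI is told when the interview ends, clinical staff contact the person promptly, the medical team is consulted within 24 hours, and an alert form is filed. The consult is free to consider the threatened person. As written in the row, all of this comes after the encounter.

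**Step 3: the other Chart A rows.**
- Medical emergency: has a 911 step, but for medical events such as chest pain or a fall from which the person cannot rise.
- Abuse: needs abuse that is disclosed or physically visible. Notifying Adult Protective Services is optional, and there is no 911 step.
- Unlocked gun: needs a gun to be found. It has no 911 step.
- Extreme home hazards: concerns the state of the dwelling.

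None of these states a 911 step for an imminent threat to another person.

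**Step 4: the rest of the protocol.**
- Sections 3.2 and 4.2 refer a PLWD who is in crisis, including danger to others, to services. This is an eligibility rule, which 4.2 applies at baseline. It does not cover care partners or threats that arise later.
- Section 7.2 trains the team to report alerts to the PI at once, but points back to Chart A for the action.
- Section 8 gives no action for danger to others after enrollment.
- Section 11.2.1.1 says that a team of experts will deal with events promptly, without giving a step.

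**The case against.** The strongest reply is that the row misdirects nobody. A promise not to hurt oneself makes little sense for someone who threatens only another person, so both branches may have been meant for self-harm alone. That reading is at least as natural as the literal one. It follows that a reader who infers that the protocol plainly routes an imminent threat to others to the physician branch goes further than the text: this holds on one reading only. On the other reading the row omits the case, and the omission remains.

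A second reply is that MCCs would call 911 anyway. They complete an eight-module certification and two half-day scenario-based sessions (Section 5.1), work in organizations with established clinical practice standards (Section 11.4), and are not told by Chart A to refrain from calling. Section 5.1 also lists an intervention handbook, a field reference guide and a scope-of-practice manual, none of them available for this review. This stands. A reader might infer that MCCs have no instruction, or that a threatened person would go unprotected, and the documents support neither inference. They also do not show that the unseen materials fill the gap, and the row contains no pointer to them.

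A third reply is that the matter is small. That also stands, and it sets the severity.

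**Conclusion.** The point holds as a drafting gap in a safety procedure. The row's label includes threats to others, while its two branch conditions and its verbal agreement name self only. For an imminent threat to another person alone, the row either leads to the physician branch or gives no immediate protective step. Nothing else in the protocol text states a 911 call for that case.

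The conclusion concerns the wording of Chart A, not what MCCs would do in practice. The frequency of such threats is not given and cannot be derived. Later escalation applies on both readings, and outcomes and analyses are unaffected. The severity is minor: this is a cheap improvement to participant safety.

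**What to change.** Amend the one row in Chart A:

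1. State that an imminent threat to self or to others triggers a 911 call.
2. Limit the lower-urgency branch to persons who are not an immediate threat to self or to others.
3. Extend the verbal agreement to not hurting others.
4. For threats to others, do not carry over the instruction to stay with the person. The MCC calls 911 from a safe place, and the clinical team sets the step for the threatened person. Adding others to the urgent condition without this change would tell an MCC to remain with someone threatening violence.

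If the handbook or field reference guide already covers the case, a cross-reference in the row is enough.

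The cost is IRB review of the modification (Section 11.1), an update to the alert training described in Section 7.2, and some clinical time to write item 4. The only IRB timing in the documents is 3-4 weeks, given for consent changes in Section 11.2.1.2; a similar time is assumed here. No added visits or data collection are needed.

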## 7.4 Adverse Events and Serious Adverse Events

### 7.4.1 Definitions

**AE Definition:** AE is any untoward or unfavorable medical occurrence in a human study participant, including any abnormal sign (e.g., abnormal physical exam or laboratory finding), symptom, or disease, temporally associated with the participants' involvement in the research, whether or not considered related to participation in the research.

**SAE Definition:** SAEs consist of any adverse event that results in death; is life threatening or places the participant at immediate risk of death from the event as it occurred; requires or prolongs hospitalization; causes persistent or significant disability or incapacity; results in congenital anomalies or birth defects; is another condition which investigators judge to represent significant hazards.

**Unanticipated Problem (UP) Definition:** any incident, experience, or outcome that meets all of the following criteria:

- unexpected, in terms of nature, severity, or frequency, given (a) the research procedures that are described in the protocol-related documents, such as the IRB-approved research protocol; and (b) the characteristics of the study population;
- related or possibly related to participation in the research; and
- suggests that the research places participants or others at a greater risk of harm (including physical, psychological, economic, or social harm) than was previously known or recognized.

#### 7.4.2 AE/SAEs for this study

**AEs for this study.** We are not anticipating any adverse medical occurrences related to participation in this research. The intervention is an enhanced usual care approach and does not introduce any components that would put subjects at risk for medical AEs.

**SAEs for this study.** Study team investigators are not anticipating serious medical events related to participation in the research. However, we do anticipate SAEs to occur based on this being an older population. The intervention is an enhanced usual care approach and does not introduce any components that would put subjects at risk for medical SAEs.

#### 7.4.3 Classification of Severity and Study Relatedness

All data and safety monitoring reporting will classify SAEs and AEs as to their severity, expectedness, and potential relatedness to the study intervention as per the definitions below:

##### Severity

- **Mild:** Awareness of signs or symptoms, but easily tolerated and are of minor irritant type causing no loss of time from normal activities. Symptoms do not require therapy or a medical evaluation; signs and symptoms are transient.
- **Moderate:** Events introduce a low level of inconvenience or concern to the participant and may interfere with daily activities, but are usually improved by simple therapeutic measures; moderate experiences may cause some interference with functioning
- **Severe:** Events interrupt the participant's normal daily activities and generally require systemic drug therapy or other treatment; they are usually incapacitating

##### Expectedness

- **Unexpected** - nature or severity of the event is not consistent with information about the condition under study or intervention in the protocol, consent form, product brochure, or investigator brochure.
- **Expected** - event is known to be associated with the intervention or condition under study.

Unexpected events will be subject to expedited reporting requirements as described in the [NIA Guidance on Clinical Trials](#).

##### Relatedness

- **Definitely Related:** The adverse event is clearly related to the investigational agent/procedure – i.e., an event that follows a reasonable temporal sequence from administration of the study intervention, follows a known or expected response pattern to the suspected intervention, that is confirmed by improvement on stopping and reappearance of the event on repeated exposure and that could not be reasonably explained by the known characteristics of the subject's clinical state.
- **Possibly Related:** An adverse event that follows a reasonable temporal sequence from administration of the study intervention follows a known or expected response pattern to the suspected intervention, but that could readily have been produced by several other factors.
- **Not Related:** The adverse event is clearly not related to the investigational agent/procedure - i.e., another cause of the event is most plausible; and/or a clinically plausible temporal sequence is inconsistent with the onset of the event and the study intervention and/or a causal relationship is considered biologically implausible.

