#### Reporting schedule:

If a serious adverse event occurs, clinic staff and investigators will be instructed to report the event to the PI who will notify the IRB and the NIA per the schedule below. The PI will provide a safety report describing the adverse event and any actions taken. The PI will keep a log of all adverse events (minor and serious) in compliance with IRB and NIH policies including whether the event is unrelated, possibly related, or probably related to the study or intervention. This log will be provided to all necessary parties as indicated below.

- All **adverse events that are serious (SAE) and unexpected** (i.e., have not been previously reported for the study's intervention) will be reported to the IMPACT Collaboratory Regulatory and Data Team Leader ([name]), NIA IMPACT Collaboratory Program Officer (PO) ([name]), and the IMPACT Collaboratory DSMB Chair or Safety Officer within 48 hours of the study's knowledge of the SAE.
  - Only those adverse events that are serious (SAE), unexpected, ***and related to the intervention*** must also be reported to Advarra IRB. Unexpected and ***unrelated*** SAEs will be reported to Advarra IRB on a case-by-case basis if requested by the IMPACT Collaboratory DSMB Chair, Safety Officer, or NIA IMPACT Collaboratory PO.
- All deaths will be reported to IMPACT Collaboratory Regulatory and Data Team Leader ([name]), NIA IMPACT Collaboratory PO ([name]), and the IMPACT Collaboratory DSMB Chair or Safety Officer within 24 hours of the knowledge of death.
  - Advarra IRB does not require the specific reporting of death outside of the SAE reporting requirement above, but they will be notified on a case-by-case basis if requested by the IMPACT Collaboratory Chair, Safety Officer or NIA IMPACT Collaboratory PO.
- All **unanticipated problems (UPs)** will be reported to the IMPACT Collaboratory Regulatory and Data Team Leader ([name]), Advarra IRB, NIA IMPACT Collaboratory PO ([name]), and the IMPACT Collaboratory DSMB Chair or Safety Officer within 48 hours of the study's knowledge of the event.

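### Section 7.4.3 defines related events by drug-type criteria that one-time serious events cannot meet, and a novel harm plausibly linked to the program fits none of its three grades

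*Combined protocol and SAP*

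**What the plan says.** The opening of 7.4.3 requires every safety report to classify AEs and SAEs by the definitions that follow it. The relatedness grades are:

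- **Definitely Related**: suitable timing, a recognized response pattern, no reasonable explanation in the participant's clinical state, and an event "that is confirmed by improvement on stopping and reappearance of the event on repeated exposure".
- **Possibly Related**: suitable timing, and the event "follows a known or expected response pattern to the suspected intervention, but that could readily have been produced by several other factors". It has no stopping or re-exposure condition.
- **Not Related**: positive grounds are needed, for example that "another cause of the event is most plausible", that the timing does not fit, or that causation is biologically implausible.

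On what the program might cause, 7.4.2 states "We are not anticipating any adverse medical occurrences related to participation in this research" and adds that the intervention "does not introduce any components that would put subjects at risk for medical SAEs". Section 7 does name a non-medical risk: "There are potential risks of discomfort about answering personal questions during the evaluation".

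Under 7.4.4, only SAEs that are unexpected and also related to the intervention "must also be reported to Advarra IRB". Footnote 3 of the summary table applies the same relatedness condition to the SAE and death columns. The adverse event log in 7.4.4, like 7.2, uses a different scale: unrelated, possibly related or probably related.

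**The concern.** The Definitely Related wording suits a drug that can be withdrawn and given again. MIND at Home is a single three-month course of assessment, care planning, referral and contact. No procedure for withdrawing and restarting it to test causality is described.

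The program can still plausibly contribute to harm. Section 5.1 includes recommendations on medication administration and home safety, and section 7 allows referral about drug therapy. Consider a fall after a home change that the Memory Care Coordinator recommended. Timing and mechanism may both fit, but the protocol lists no response pattern to match it against.

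Relatedness decides whether an unexpected SAE goes promptly to the IRB, and it is one of the conditions for an unanticipated problem. Consent is to be waived, and section 11.2 cites the adverse event monitoring process in support of that waiver. The classification rule should therefore be able to record a related serious event if one occurs.

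**Working it through.** No arithmetic applies. The check sets the conditions of each grade beside the routes that depend on them.

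1. **Definitely Related, serious events.** The conditions are joined, so all must hold. A death cannot improve on stopping or recur. A completed hospitalization is over, and nothing in the plan withdraws and restarts the program to see whether it happens again. For one-time serious events the grade is effectively unusable.

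2. **Possibly Related, serious medical events.** No stopping or re-exposure is needed, but a recognized pattern is. Section 7.4.2 supplies none for medical events. Section 7 names discomfort and loss of confidentiality, which would not ordinarily meet the SAE definition in 7.4.1.

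3. **Possibly Related, non-serious events.** This grade can be reached. Distress during the needs assessment is a named risk, and 7.1 says "participants may decline to answer any questions, take frequent breaks, or stop the assessment". Contacts recur at least every 30 days (5.1), so even improvement on stopping and recurrence are conceivable for such distress.

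4. **Unexpected and related together.** Under Expectedness in 7.4.3, *unexpected* means a nature or severity at odds with the protocol's information on the condition or intervention. *Related* requires a pattern already recognized. A harm new in nature cannot be both. What remains is a known pattern of unexpected severity. Section 7.4.4 also glosses *unexpected* as not previously reported for the intervention. That formally admits an effect foreseen but never yet seen, but the protocol foresees no serious one.

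5. **Harms left without a grade.** Take an event with fitting timing, a plausible mechanism, no recognized pattern and no likelier cause. It fails both related grades for want of a pattern. It fails Not Related because none of the positive grounds applies. It belongs to none of the three.

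6. **Routes, side by side.**

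| Route | Relatedness needed | Affected? |
|---|---|---|
| Expedited IRB report of unexpected SAEs (7.4.4, footnote 3) | Related; whether possibly related counts is not stated | Yes, nearly empty |
| Serious events to IRB, DSMB Chair and Safety Officer (7.2) | Possible or potential | Not empty; conflicts with 7.4.4 |
| Unanticipated problems (7.4.1, 7.4.4) | Possibly related is enough | Not empty; novel harms blocked only if the 7.4.3 definition governs the term |
| Unexpected SAEs within 48 hours and deaths within 24 hours to the IMPACT team lead, NIA program officer, and DSMB Chair or Safety Officer (7.4.4) | None | No |
| Summaries to the same parties and the IRB at least every 6 months (7.4.4) | None | No |

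7. **Scales.** Probably related appears in 7.2 and in the 7.4.4 log but is not defined in 7.4.3. Definitely Related is defined in 7.4.3 but is absent from the log scale.

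**The case against.** The strongest reply is that oversight does not rest on this wording. Unexpected SAEs and all deaths reach the program officer and the DSMB Chair or Safety Officer whatever their grade, and those parties can ask that unrelated events go to the IRB. Section 7.2 separately sends possibly related serious events to the IRB. Classification is also a judgment made by the study team, and 7.4.2 states what is anticipated rather than how to classify. All of this stands, and it limits the consequence. It does not remove the defect, because 7.4.3 says reports follow its definitions and the other sections do not override them.

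Three stronger readings are tempting, and the documents do not support them.

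- A reader might infer that no event can ever be related. The stopping and re-exposure clause sits in one grade only, and assessment distress can be Possibly Related.
- A reader might infer that every route depending on relatedness stays empty. The 7.2 and unanticipated-problem routes accept possibly related events.
- A reader might size the problem by the admissions to be expected in 150 patients. Section 7 already treats hospitalizations and deaths as expected in this population. Such a count would measure background events, not misclassified ones.

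Nor does any section say that a count of zero related SAEs will be carried into the full trial as a safety claim.

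**Conclusion.** Wrong as written, minor severity. For one-time serious events Definitely Related is effectively unusable. The pattern requirement in both related grades pulls against *unexpected*, so the expedited IRB route for unexpected, related SAEs is nearly empty on a literal reading. A novel, plausible harm with no likelier cause has no grade.

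The size cannot be put as a number: the documents give no rate of program-related harm, and the number of events affected may be small in a low-risk, unrandomized pilot. The conclusion assumes that 7.4.3 is applied as worded and that the NIA-approved reporting form, which is not in the documents, does not replace its definitions.

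**What to change.** In 7.4.3:

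- Delete the stopping and re-exposure clause, and the response-pattern clause in both related grades.
- Define the related grades by a reasonable temporal sequence plus a plausible link to a program action, such as the needs assessment, a care-plan recommendation or a referral.
- Keep the grades distinct by whether other causes could readily explain the event.
- Make Not Related the complement, so that every event falls in exactly one grade.

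Elsewhere:

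- Use one scale in 7.2, 7.4.3 and the 7.4.4 log, settling probably versus definitely.
- State in 7.4.4 and footnote 3 whether possibly related triggers the IRB report, and reconcile this with 7.2 and with the unanticipated-problem definition in 7.4.1.

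The cost is rewording one subsection, aligning the related text and updating the form instructions. The downside is that a few more events may be classed as possibly related and need IRB reporting.
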